6.2. Efficacy Endpoints

Unless otherwise specified, the efficacy evaluation period will be the observation period in Section 2.2. The number of days from the start date of treatment to the onset date of event will be calculated as [event onset date – start date of treatment with this drug + 1]. In the analyses related to the end date of the observation period, the primary definition of the end date will be up to Day 28 after the end of treatment, and the secondary definition will also be defined for evaluation (Section 10.2 Table 2).

The following efficacy endpoints are defined for Efficacy Analysis Sets 1, 2, and 3.

• Worsening of severity of infection caused by SARS-CoV-2: Whether the severity of infection caused by SARS-CoV-2 has worsened will be evaluated. However, when the severity is severe at the start of this drug and does not worsen during the observation period, it will be considered as "severe at the start of treatment." Otherwise, if the date of the highest severity is the day after the end of the evaluation period or later, it will be handled as "unknown (highest severity recorded after the end of evaluation period)." Therefore, the categories will be as follows. "Worsened" will be considered as an

event. The expected entries in the CRF and their handling, and assessment of endpoints are shown in Section 10.3 Table 3.

- Not worsened, worsened, severe at the start of treatment, unknown (highest severity recorded after the end of the evaluation period, worsening unknown, no record of worsening)
- Highest severity: The highest severity will be evaluated for patients with the above worsening of severity of infection caused by SARS-CoV-2. If the highest severity is unknown but the severity is considered to have worsened, the highest severity will be "moderate II or severe (indistinguishable)" for patients with the initial severity of moderate I and as "severe" for patients with the initial severity of moderate II. It consists of the following categories. The expected entries in the CRF and their handling, and assessment of endpoints are shown in Section 10.3 Table 3.
 - Mild, moderate I, moderate II, severe, moderate II or severe (indistinguishable), unknown (severity unknown, severity not recorded)
- Highest severity (moderate II or severe): For patients with the above worsening of severity of infection caused by SARS-CoV-2, the highest severity of moderate II, severe, and moderate II or severe (indistinguishable) will be defined as "moderate II or severe" and evaluated as an event. If the highest severity is unknown but the severity is considered to have worsened, the highest severity will be "moderate II or severe (indistinguishable)" and "severe" for patients with the initial severity of moderate I and moderate II, respectively, and the patient will be considered to have experienced an event.
- Presence/absence and severity of symptoms as of the end date of the observation period: It consists of the following categories:
 - No symptoms, symptoms present (mild, moderate I, moderate II, severe, severity unknown), unknown (symptoms unknown, symptoms not recorded)
- Resolution of symptoms from the start of treatment with this drug as of the end date of the observation period: The absence of symptoms on the end date of the observation period in patients with symptoms at the start of treatment with this drug will be considered as resolution of symptoms and evaluated. If the patient has no symptoms at the start of treatment with this drug, the patient will be considered to have no symptoms at the start of treatment. It consists of the following categories. The expected entries in the CRF and their handling, and assessment of endpoints are shown in Section 10.3 Table 4.
 - Resolved, not resolved, no symptoms at the start of treatment, unknown (resolution unknown, symptoms not recorded)
- Improvement in severity from the start of treatment with this drug as of the end date of the observation period: The improvement in severity from the start of treatment with this drug on the end date of the observation period will be evaluated. It consists of the following categories. The expected entries in the CRF, their handling, and assessment of endpoints are shown in Section 10.3 Table 5.

- Improved, not improved, no symptoms at the start of treatment, unknown (improvement unknown, severity not recorded)
- Resolution of symptoms after worsening of severity during the observation period as of the end date of the observation period: For patients with worsening of severity during the observation period, the absence of symptoms on the end date of the observation period will be considered as resolution of symptoms and evaluated. It consists of the following categories. Even if the end date of the observation period and the date of the highest severity are the same, the patient will be included in the analysis.
 - Resolved, not resolved, unknown (resolution unknown, symptoms not recorded)
- Improvement in severity after worsening of severity during the observation period as of the end date of the observation period: For patients with worsening of severity during the observation period, improvement from the highest severity on the end date of the observation period will be evaluated. It consists of the following categories. Even if the end date of the observation period and the date of the highest severity are the same, the patient will be included in the analysis.
 - Improved, not improved, unknown (improvement unknown, severity not recorded)
- Death from any cause: Death reported by Day 28 after the end of treatment will be considered as an event and evaluated. Death should be confirmed with the outcome information of adverse events. Unknown if no adverse event is reported (Section 10.1 Table 1).
 The number of days from the start date of treatment to the onset date of event will be calculated. If an event including the case of unknown has not occurred, the patient will be censored at the date of the last observation or Day 28 after the end of treatment, whichever is earlier.

The following efficacy endpoint is defined in Efficacy Analysis Sets 2 and 3.

• Hospitalization for the treatment of infection due to SARS-CoV-2 or death from any cause: Hospitalization for treatment of infection caused by SARS-CoV-2 or death reported by Day 28 after the end of treatment will be considered as an event and evaluated. Death should be confirmed with the outcome information of adverse events. Unknown if neither the status of hospitalization nor the presence or absence of adverse events is reported. When only the status of hospitalization or the presence or absence of adverse events is reported and hospitalization or death applicable to an event is observed, it will be considered as an event, and other cases will be regarded as unknown (Section 10.1 Table 1). In addition, each event of hospitalization and death will be evaluated.

The number of days from the start date of treatment to the onset date of event will be calculated, but the onset date of event will be the earlier date of hospitalization or death. Even if only either the status of hospitalization or the presence or absence of adverse events is reported, the date of hospitalization or death will be regarded as the onset date of event if hospitalization or death applicable to an event is confirmed. If the status of hospitalization is not reported and death is observed, it is acceptable to consider the date of death as the onset date of event because the status of hospitalization is unknown, although it may overestimate the time to event. If no event has occurred, the patient will be censored at the date of the last observation or Day 28 after the end of treatment, whichever is earlier. Even in

the case of unknown, the patient will be censored at the start date of treatment if neither the status of hospitalization nor the presence or absence of adverse events is reported and if the status of hospitalization is not reported and the patient has not died, or at the date of last observation or Day 28 after the end of treatment, whichever is earlier, if the presence or absence of adverse events is not reported and the patient has not been hospitalized.

- For the purposes of sensitivity analysis, hospitalization for the treatment of infection caused by SARS-CoV-2 is defined as follows. For hospitalizations not meeting this, the patient will be censored according to the above definition.
 - There are concomitant medications for infection caused by SARS-CoV-2 or concomitant non-drug therapies due to infection caused by SARS-CoV-2 on or after the date of admission.

Concomitant medications for infection caused by SARS-CoV-2 are as follows: remdesivir (Veklury), molnupiravir (Lagevrio), dexamethasone, baricitinib (Olumiant), casirivimab/imdevimab (Ronapreve), sotrovimab (Xevudy), tocilizumab (Actemra), tixagevimab/cilgavimab (Evusheld), and ensitrelvir fumarate (Xocova). * Categories will be set appropriately for drugs for the treatment of infection caused by SARS-CoV-2 in addition to the drugs listed.

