#### 8.3.8. End-of-study / Discontinuation record

The end date of the observation period (date of medical examination on or after Day 28 after the completion of administration) should be recorded. If the patient cannot be followed up until Day 28 after the completion of administration (including Day 28), record date of discontinuation and select only one of the following items that corresponds to the primary reason. If the primary reason corresponds to patient death, necessary information should be recorded in the adverse event field.

- 1. End date of the observation period (date of examination on or after Day 28 after the completion of administration or date of discontinuation)
- Status at the end
  - Completed
  - Symptoms improved
  - Death

- Transferred to other hospital
- Lost to follow-up
- Other

However, if the patient does not return for follow-up visit after the start of administration (including confirmation by telephone, etc.), the information should be recorded in the "lost to follow-up."

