# 8.3.9. Effectiveness evaluation (severity)

The presence/absence of worsening of the severity of infections caused by SARS-CoV-2 after administration of this drug during the observation period (until Day 28 after the completion of administration [including Day 28]), highest severity, and presence/absence and severity of symptoms on the end date of the observation period (date of medical examination on or after Day 28 after the completion of administration) should be entered. For cases discontinuing observation in less than 28 days after the completion of administration, the highest severity by that point and the severity as of the date of discontinuation of the observation period should be recorded (see Table 2 for severity).

- 1. Worsening of severity after administration
  - Presence/absence of worsening of symptoms
  - Date of highest severity
  - Highest severity
- 2. Severity on the end date of the observation period
  - Date of evaluation
  - Presence/absence of symptoms of infections caused by SARS-CoV-2
  - Severity

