10.2. Appendix 2: Data Extraction Details

 Table 2.
 Definitions of Acceptable Windows for Timing

Timing	Endpoint	Definition [acceptable window]
At the start of treatment	Efficacy endpoints, viral load, body temperature, percutaneous arterial oxygen saturation	From 30 days prior to the date of first dose in this study (start date of treatment) to the start date of treatment
During the observation period	Safety endpoints, efficacy endpoints, viral load, body temperature, percutaneous arterial oxygen saturation, concomitant drug therapy, and non-drug therapy	Start date of treatment to Day 28 after the end of treatment
End date of the observation	Efficacy endpoints	Primary definition: Up to Day 28 after the end of treatment
period		Secondary definition 1: Up to 42 days after the end of treatment
		Secondary definition 2: Entire period

10.3. Appendix 3: Data Entries Related to Efficacy Endpoints and Their Handling, and Assessment of Endpoints

Table 3. Worsening of Severity and Highest Severity of Infection Caused by SARS-CoV-2

Symptoms	Severity at			Worsening of	of severity: H	ighest sev	erity			
at the start of	the start of treatment	Worsening	Vorsening of severity during the observation period							
treatment	with this	Absent		Present						
with this	drug	Highest seve	erity	ity						
drug		NA	Mild	Moderate I	Moderate II	Severe	Unknown	NA		
Absent	NA	Absent: NA	Present: Mild	Present: Moderate I	Present: Moderate II	Present: Severe	Present: Unknown	Unknown: NA		
Present	Mild		Case 1				Case 2			
	Moderate I									
	Moderate II									
	Severe	Severe at the start: NA	Case 3							
	Unknown	Absent: NA	Case 4							
Unknown	NA	Case 5								

NA: not applicable

Discrepancies between evaluations at the start of treatment with this drug and during the observation period are subject to re-investigation, but the reasons for being subject to re-investigation and handling of cases where there is no change as a result of re-investigation are shown below.

- Case 1: Assessed as "Unknown: NA" because the highest severity is lower than the severity at the start of treatment with this drug.

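### The end-of-observation proportions pool status at early exit with status at about Day 28, and no planned analysis separates the two

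*SAP*

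**What the plan says.** Day 28 here is counted from the day after the last dose.

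**Windows.** SAP 6.2 says that "the primary definition of the end date will be up to Day 28 after the end of treatment". SAP Table 2 (Appendix 2) lists all three end-date windows: "Primary definition: Up to Day 28 after the end of treatment", "Secondary definition 1: Up to 42 days after the end of treatment" and "Secondary definition 2: Entire period".

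**What the end date is.** Protocol 8.3.8 has the site record "End date of the observation period (date of examination on or after Day 28 after the completion of administration or date of discontinuation". For patients who leave before Day 28, Protocol 8.3.9 says "the highest severity by that point and the severity as of the date of discontinuation of the observation period should be recorded". The end-status list in Protocol 8.3.8 includes "Symptoms improved" alongside death, transfer to another hospital and loss to follow-up.

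**How the outcome is scored.** SAP 6.2 defines resolution as "The absence of symptoms on the end date of the observation period in patients with symptoms at the start of treatment with this drug". Improvement compares severity on the end date with severity at the start of treatment. The two endpoints that follow a worsening are read from the same date. SAP Tables 4 and 5 apply these rules with no condition on the day of evaluation and no category for observation that ended early. Under SAP 7, a value is missing only if nothing falls inside the window.

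**What is planned around it.** SAP 8.2.4 repeats the efficacy analyses under the secondary definitions, but not for subgroups. SAP 8.2.4.7 estimates the subgroup risk ratios for resolution and improvement over the entire period only. SAP 8.2.1.2 tabulates discontinuation by timing, starting with the treatment phase, and by reason.

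**The concern.** An end-date proportion from a study with a fixed 28-day follow-up will normally be read as status at about Day 28. Here it is status on whatever day the site stopped observing. A patient discharged from follow-up on Day 4 as improved, a patient transferred on Day 2 while symptomatic and a patient examined on Day 28 all count equally.

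The day is also not chosen independently of the result. Improvement, death and transfer all end observation early, and each is linked to the status then recorded.

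Exact confidence intervals are planned for the resolved and improved proportions, and risk ratios for subgroups. The intervals describe sampling error around this mixture. The risk ratios can differ from one merely because subgroups leave at different times or for different reasons.

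**Working it through.** The plan gives no figure for early exit, resolution or day of examination, so there is no stated number to reproduce. The first two steps are readings of the text. The rest are illustrations on stated assumptions.

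**1. Lower limits.** The upper limits of the three windows are Day 28, 42 days and none. The lower limits are none, none and none. A value recorded on a discontinuation date before Day 28 is therefore inside every window, and moving to a secondary definition never removes it.

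**2. Completers in the primary window.** Completers are examined on Day 28 or later (Protocol 8.3.8), but the primary window closes at Day 28. The only day that satisfies both is Day 28 itself. A completer seen on Day 29 has no value in the window and becomes missing under SAP 7, while early leavers are kept.

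**3. Share of values from early leavers.** Let S be the share leaving early and f the share of completers examined exactly on Day 28, and assume that everyone has an end-date value recorded.

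- Primary window: share = S / (S + (1 − S) × f)
- Entire period: share = S

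| S | f = 1 | f = 0.5 | f = 0.1 | Entire period |
|---|---|---|---|---|
| 10% | 10% | 0.10/0.55 = 18% | 0.10/0.19 = 53% | 10% |
| 30% | 30% | 0.30/0.65 = 46% | 0.30/0.37 = 81% | 30% |

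The entire-period definition brings the share down to S, and no further.

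**4. Effect on the reported proportion.** Assume that true Day 28 resolution is 90% in leavers and completers alike and that all completers are counted. Let e be the share leaving early and p the share of leavers who are symptom-free at exit. Reported = (1 − e) × 0.90 + e × p.

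- e = 0.10, p = 0.5: 0.81 + 0.05 = 86%
- e = 0.20, p = 0.5: 0.72 + 0.10 = 82%
- e = 0.05, p = 0.7: 0.855 + 0.035 = 89%
- e = 0.10, p = 1.0: 0.81 + 0.10 = 91%
- e = 0.20, p = 1.0: 0.72 + 0.20 = 92%

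The error runs from −8 to +2 points, and its sign depends on p.

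**5. Dependence on exit reasons.** Let 30% leave early. Count those who leave for improvement as 100% resolved and other leavers as 30% resolved, and let completers resolve at 85% or 95%.

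- Half leave for improvement: leavers are 0.5 + 0.5 × 0.3 = 65% resolved. The pooled figure is 0.7 × 0.85 + 0.3 × 0.65 = 79.0% or 0.7 × 0.95 + 0.3 × 0.65 = 86.0%, which is 6.0 or 9.0 points below completers.
- 90% leave for improvement: leavers are 0.9 + 0.1 × 0.3 = 93% resolved. The pooled figure is 87.4% or 94.4%, which is 2.4 points above or 0.6 points below completers.

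The reasons for leaving decide the direction, and no planned table crosses them with outcome.

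**The case against.** The strongest reply is that the SAP does what the protocol asks. Protocol 8.7 plans tabulation by severity on the end date, and the protocol itself admits the discontinuation date as an end date. The values are real evaluations made on that date. A reader might infer that this is last observation carried forward, but that holds only if a Day 28 target is presumed, and the documents name no such target. What remains is a problem of mixed timing and of what the proportion means.

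A reader might also infer that the secondary definitions are useless here. They are not. They bring back completers seen after Day 28 and so dilute the early-leaver share, as step 3 shows. They do not remove it.

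A third tempting reading is that the plan understates resolution by more than its sampling error. The documents do not support this. The sign reverses when most leavers are well at exit. A half-width of about 1.1 points (1.96 × √(0.9 × 0.1 / 3000)) also borrows the safety-set target of 3000, which is not the number of symptomatic patients in an efficacy set.

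Some of the ground is covered. Discontinuation timing and reason are tabulated in each efficacy set, efficacy evaluations are listed (SAP 9), and death and hospitalization-or-death use censored time-to-event methods. The study is single-arm and non-confirmatory (SAP 4). These points limit the consequence, but none of them shows resolution or improvement separately for patients who left early.

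**Conclusion.** The point stands as one of undefined timing. It does not establish a bias of known sign. No end-date window has an earliest day, early-exit status enters all of them, and the exit reasons are linked to outcome. The primary window compounds this by dropping completers examined after Day 28. The subgroup risk ratios avoid that last defect by using the entire period, but they still include early leavers.

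The size depends on rates the documents do not give. Early leavers make up 46% of primary-window values if 30% leave and half of completers are seen after Day 28. They make up 10% if 10% leave and every completer is seen on Day 28. Against an assumed true 90%, with 10% to 20% leaving, the reported resolution lies between 82% and 92%. If few patients leave early, the effect is small.

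It is worth correcting because it changes what the proportions can be taken to mean and the remedy is cheap. It does not call the death or hospitalization analyses into question.

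**What to change.** Keep the planned end-date tabulation and add the following.

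1. Split each end-date endpoint into patients observed to Day 28 or later and patients whose observation ended before Day 28. Break the second group down by the end statuses in Protocol 8.3.8.
2. Tabulate the day of evaluation.
3. Give the proportion and exact interval for each part as well as for the total.
4. Apply the same split to the subgroup risk ratios for resolution and improvement, as a sensitivity analysis.
5. Reconcile the primary window in SAP 6.2 and Table 2 with the examination timing in Protocol 8.3.8, so that completers are not dropped.

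Do not make the proportion among patients evaluated near Day 28 the only headline. If leaving depends on outcome, that figure selects on staying. Under the present upper limit it could also rest on few patients.

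The dates and end statuses are already collected, so the cost is SAP wording and one extra table with smaller denominators. Items 1 to 4 leave the endpoint definitions unchanged. Item 5 may count as a significant modification, which Protocol 8.7 says must also be reflected in a protocol amendment. Any addition made after data have been seen should be labelled post hoc.

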2.2. Study Design

This is a multicenter cohort study to be conducted in patients treated with this drug. The case report form (CRF) will be filled out based on the medical records containing data obtained in usual clinical practice.

The subjects of the study are patients who have received this drug for the first time, which is a registration condition.

The observation period will be from the start date of treatment to Day 28 after the end of treatment (the day following the end of treatment is defined as Day 1).

"Indications" and "dosage and administration" in the package insert (prepared in February 2022 [Version 1]) are as follows:

• Indications: Infection caused by SARS-CoV-2

• Dosage and administration: The usual dosage for adults and children aged 12 years or older with body weight of 40 kg or more is 300 mg of nirmatrelvir and 100 mg of ritonavir administered orally at the same time twice daily for 5 days.

The target sample size is 3000 patients as the safety analysis set. The incidence of adverse reactions to this drug in the phase 2/3 study (Study C4671005) was 7.8%. Assuming that the incidence of adverse reactions is the same in the actual use in Japan, adverse reactions will be detected in at least 214 patients with a probability of 90% with a sample size of 3000 patients. In order to detect, with a probability of 95%, at least 1 unknown adverse reaction occurring at a frequency of 0.1% or more, 3000 patients are required.

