10. APPENDICES

10.1. Appendix 1: Handling of Efficacy-related Questionnaire Items in the Identification of Efficacy Analysis Sets

Table 1. Identification of Efficacy Analysis Sets 1 and 2

Case	Stat	Status of CRF entry		Safety Analysis Set‡	Efficacy	Efficacy Analysis Set 1†‡		Efficacy Analysis Set 2†‡			
	Adverse	Hospitali	Efficacy	Inclusion/	Inclusion/	Eval	uable	Inclusion/		Evaluable	
	event page	zation status page	evaluatio n page	exclusion (Reason)	exclusion (Reason)	Deaths	Severity related	exclusion (Reason)	Deaths	Hospitalization or death	Severity related
1	Yes	Yes	Yes	Included	Included	Yes	Yes	Included	Yes	Yes	Yes
2	No	Yes	Yes	Excluded (AE information)	Included	Unknown	Yes	Included	Unknown	Yes (only hospitalization events present) or unknown	Yes
3	Yes	No	Yes	Included	Included	Yes	Yes	Included	Yes	Yes (only death events present) or unknown	Yes
4	Yes	Yes	No	Included	Included	Yes	Unknown	Included	Yes	Yes	Unknown
5	No	No	Yes	Excluded (AE information)	Included	Unknown	Yes	Included	Unknown	Unknown	Yes
6	No	Yes	No	Excluded (AE information)	Included	Unknown	Unknown	Included	Unknown	Yes (only hospitalization events present) or unknown	Unknown
7	Yes	No	No	Included	Included	Yes	Unknown	Included	Yes	Yes (only death events present) or unknown	Unknown
8	No	No	No	Excluded (AE information)	Excluded (Efficacy information)	NA	NA	Excluded (Efficacy Set 1)	NA	NA	NA

AE, adverse event; NA, not evaluated due to exclusion from population

[‡] For the CRF pages to be used to identify the population other than the adverse event page, hospitalization status page, and efficacy evaluation page, it is assumed that there are no items meeting the exclusion criteria.

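### A patient known to have died but with no efficacy entry is classed 'unknown' for worsening, resolution and improvement; probably few patients, and cheap to repair

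*SAP*

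**What the plan says.** SAP 6.2 gives worsening the categories "Not worsened, worsened, severe at the start of treatment, unknown" and spells out the last as "unknown (highest severity recorded after the end of the evaluation period, worsening unknown, no record of worsening". Only the worsened category is an event. Resolution of symptoms has "Resolved, not resolved, no symptoms at the start of treatment, unknown (resolution unknown, symptoms not recorded", and improvement in severity follows the same pattern. None of them has a category for death. Nor does the severity scale in Protocol 8.3.1, Table 2, whose top grade is ICU admission or mechanical ventilation.

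SAP 10.1, Table 1 sets the handling by which CRF pages are filled in. In cases 4 and 7 the adverse event page is present and the efficacy page is absent. Both cases stay in Efficacy Analysis Sets 1 and 2, with death evaluable and the severity endpoints unknown. The hospitalization-or-death column treats a known death differently. In cases 3 and 7, where the hospitalization page is missing, the entry is "Yes (only death events present) or unknown", so a recorded death counts as an event even though the other component is not known.

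Death is read from the adverse event outcome (SAP 6.2), and Protocol 8.3.8 sends information on a death to the adverse event field. SAP 7 does not impute missing efficacy values. SAP 8.2.4.1 plans a confidence interval for the worsened proportion and uses patients with worsening as the denominator for highest severity. The general sensitivity analysis in SAP 8.2.4 changes only the evaluation window.

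**The concern.** A blank efficacy page in a patient known to have died is not the same as a blank page in a patient about whom nothing is known. The plan puts both in one category. If the death was due to the infection, the worst outcome on this endpoint is missing from the worsened numerator, and the reason it is missing may be the outcome itself. Highest severity is affected more directly: a patient not classed as worsened is in neither its numerator nor its denominator. The risk ratios for worsening in SAP 8.2.4.7 inherit the same classification.

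The plan is also uneven. It lets a known death settle the hospitalization-or-death endpoint when the other page is missing. For severity it infers a grade from partial data: a patient who starts at moderate II and is judged to have worsened to an unrecorded grade becomes severe. A known death gets no comparable rule in the severity endpoints.

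**Working it through.** **The rule in the text.** Take a patient whose adverse event outcome is fatal before Day 28 after the end of treatment and whose efficacy page is blank.
- Table 1, case 4 or 7: in Efficacy Analysis Set 1; death evaluable; severity endpoints unknown.
- SAP 6.2: no record of worsening means unknown; no symptom or severity record at the end date means unknown, unless the patient had no symptoms at the start (Tables 4 and 5 keep that category).
- SAP 7, SAP 8.2.4 and Appendix 3, Tables 3 to 5: no rule carries the death across.

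**The plan's own figures.** The documents give no rate for worsening, death or missing efficacy pages. Their only figures are for sample size (SAP 2.2): "The target sample size is 3000 patients as the safety analysis set", with at least 214 patients with adverse reactions at 90% probability. With X binomial (3000, 0.078), P(X ≥ 214) = 0.920, and the largest count with probability of at least 0.90 is 215. For the rare reaction, 1 − 0.999^3000 = 0.9503. Both are reproduced closely enough, and neither bears on this point.

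**Worsened, by illustration.** All rates here are assumptions: Set 1 has N = 3000; recorded worsening W is 1% to 5%; there are 6 to 30 deaths; 25% to 100% of them have no efficacy entry, giving k = 2 to 30. Every such death is taken not to be classed as worsened already.
- Planned proportion: W/N.
- Worsened or died without an entry: (W + k)/N.
- Share of those events missed: k/(W + k).

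| W | k | Planned (exact 95% CI) | With the k deaths (exact 95% CI) | Ratio |
|---|---|---|---|---|
| 30 | 2 | 1.00% (0.68–1.42) | 1.07% (0.73–1.50) | 1.07 |
| 30 | 30 | 1.00% (0.68–1.42) | 2.00% (1.53–2.57) | 2.00 |
| 60 | 8 | 2.00% (1.53–2.57) | 2.27% (1.76–2.86) | 1.13 |
| 60 | 30 | 2.00% (1.53–2.57) | 3.00% (2.42–3.67) | 1.50 |
| 150 | 2 | 5.00% (4.25–5.84) | 5.07% (4.31–5.91) | 1.01 |
| 150 | 30 | 5.00% (4.25–5.84) | 6.00% (5.18–6.91) | 1.20 |

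Share missed with W = 30 and k = 3, 5, 10: 3/33 = 9%, 5/35 = 14%, 10/40 = 25%. With W = 60: 3/63 = 5%, 5/65 = 8%, 10/70 = 14%.

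**Highest severity.** Assume 60 worsened, 24 of them moderate II or severe: 24/60 = 40%. If k deaths were added as severe, the share would be (24 + k)/(60 + k): 30/66 = 45%, 39/75 = 52% and 54/90 = 60% for k = 6, 15 and 30.

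**Resolved.** Assume 2700 of 3000 resolved. With unknowns in the denominator the proportion is 90.0% whatever k is. With the k deaths removed it is 2700/(3000 − k): 90.2%, 90.5% and 90.9% for k = 6, 15 and 30.

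**The case against.** The strongest reply is that the protocol already asks for the missing entry. Protocol 8.3.9 wants the highest severity so far and the severity at discontinuation when observation ends before Day 28, death is a listed end status in 8.3.8, and the sponsor can query the CRF (8.6.5.2). A patient who deteriorated and died should have an entry and be classed by it, up to severe. This stands as a limit on the number affected. It does not remove the gap: Protocol 8.9 concedes that specified data may be missing, SAP 7 sets unsigned or inconsistent entries to missing, and Table 1 provides cases 4 and 7 for patients with no efficacy page.

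A reader might infer that deaths disappear from the efficacy analysis. They do not. The patients are counted as unknown; death has its own Kaplan-Meier analysis in Sets 1 to 3, belongs to the composite in Sets 2 and 3, and is listed. None of this changes the worsened or highest-severity proportions, and inpatients in Set 1 have no composite.

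A reader might also infer that every such death is a missed worsening. The endpoint is severity of the SARS-CoV-2 infection, and a death from another cause need not be worsening of it. Nor is every patient who died necessarily unresolved: symptoms may have gone before an unrelated death, and a recorded entry saying so should stand.

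Finally, the study is single-arm and descriptive with no decision rule, and the dagger note to Table 1 is not in the text available. No visible wording reverses the classification.

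**Conclusion.** The point holds in a limited form. For a patient known to have died by Day 28 after the end of treatment who has no efficacy entry, the plan records unknown for worsening and for highest severity, and also for resolution and improvement unless the patient had no symptoms at the start. Worsened is understated to the extent that such deaths were due to the infection, and highest severity omits them from numerator and denominator.

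Two further readings are tempting but unsupported. One is that resolved and improved are overstated. That follows only if unknowns leave the denominator; SAP 8.2.4.3 plans a proportion for each category, unknown is one of the categories, and SAP 8.2.4.1 names a restricted denominator where it wants one. The other is that the loss concentrates in older or higher-risk subgroups; this is plausible, but no figure in the documents shows it.

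The size cannot be derived. On the assumed rates the ratio runs from 1.01 to 2.00, and the upper end needs 30 deaths, none with an entry, against 30 recorded worsenings. With Protocol 8.3.9 followed, the effect should lie towards the lower end. This is a worthwhile low-cost improvement, not a flaw that undermines the study.

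**What to change.** 1. In SAP 6.2 and 8.2.4.1, keep worsened as defined. Add, for Efficacy Analysis Sets 1, 2 and 3, a row for patients who worsened or died from any cause by Day 28 after the end of treatment, with its exact 95% confidence interval. Take death from the adverse event outcome even when the efficacy page is blank. Highest severity keeps its denominator; the new row shows the deaths that it does not cover.
2. For resolution and improvement, class a patient who died by the window limit and has no end-date symptom or severity entry as not resolved and not improved, or show the patient as died. Do not overwrite a recorded entry or the category for patients without symptoms at the start.
3. Keep unknown for patients not known to have died, including those without an adverse event page, and state that unknowns stay in the denominator.
4. Carry the same rules into Table 1 and Tables 3 to 5.

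The cost is SAP wording and one derived variable from data already collected. The downside is that deaths unrelated to the infection enter the added row, which is why worsened alone stays beside it.
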